7.12 Safety Evaluations

Safety assessments will include monitoring of available assessments of vital signs, adverse events (AEs), clinical laboratory tests, and physical examinations. The main analysis period would be the Treatment Emergent period which is defined as the period from the date of the first dose until the end of earliest of the following 1) date of Study Day 58 for AEs and date of Study Day 90 for the rest; or 2) date of early discontinuation from study; or 3) data cutoff date. This analysis period will be used for all treatment emergent adverse event, laboratory evaluations. However, serious adverse events analysis will include all the serious adverse events collected after the first dose.

Safety variables will be tabulated and presented for all patients in the Safety Population.

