7.1.3 Analysis Period

The main analysis period would be the Treatment Emergent period.

For all treatment emergent adverse events, it is defined as the period from the date of the first dose until the earliest of the following 1) date of Study Day 58; or 2) date of early discontinuation from study, or 3) data cutoff date. However, SAEs will include all the serious adverse events collected after the first dose.

The analysis period used for abnormalities in laboratory evaluations is defined as the period from the date of the first dose until the earliest of the following 1) date of Study Day 90; or 2) date of Early discontinuation from study, or 3) data cutoff date.

Analysis period for efficacy parameters would be the period from the date of the first dose until the earliest of the following 1) Date of Study Day 90; or 2) Date of Early discontinuation from study, or 3) data cutoff date.

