7.11.2.2 Mortality

Survival status will be collected up to Day 90 +/- 30 days. Death is considered as an event. All the mortality events and cause of death will be listed by treatment arm and by patient.

Patients who did not experience death within the first 90 days will be censored on the date of Day 90 visit or the date of last contact from the study which ever is earlier.

The number of patients who died and survival time will be summarized by treatment arm. Survival time will also be listed by patient. The probability function of death will be estimated by Kaplan-Meier method. The median time and its 95% confidence interval for each group will be reported. Cumulative progression rates estimated by the KM method for up to day 6, 14, 28, 90 and the 95% confidence intervals will be reported.

The hazard ratio will be estimated by the Cox proportional hazards model with treatment arm as a covariate in the model. Relevant hazard rates, hazard ratio between treatment arms and associated p-values will be tabulated.

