7.12.1 Adverse Event

All adverse events will be coded using Medical Dictionary for Regulatory Activities (MedDRA) version 23.0 (or later). Adverse events will be categorized as prior events, treatment emergent adverse events, and post treatment adverse events:

- Prior Events includes all adverse events with a start date before the first dose of the study drug regardless of the end date.
- Treatment-emergent adverse events (TEAE) are defined as adverse events with a start date (or date of worsening) on or after the first dose of the study drug and no later than the earliest of the following 1) the date for the Day 58; 2) date of early discontinuation from study, or 3) data cutoff date.
- All adverse event started after study day 58 will be considered post-treatment.

All TEAE will be summarized by treatment arm and presented by:

- 1) system organ classification and preferred term (PT);
- 2) PT;
- 3) system organ classification, PT and the maximum severity.

Treatment-related TEAE, serious TEAE and treatment-related serious TEAE will be summarized by MedDRA System Organ Class and PT, and the maximum severity. SAEs and deaths will be listed by patient.

For patients at sites where Aerogen devices were supplied by PTX, the following analyses will be performed:

- All device-related TEAEs will be summarized by treatment arm;
- All device-related TE-SAEs will be summarized by treatment arm;
- All device-related AEs will be listed by patient.

The frequency of treatment-emergent serious adverse events (TESAEs) will be summarized by arm, SOC, and preferred term. Severity (using CTCAE) and relationship of TEAEs to treatment (sargramostim, sargramostim inhalation device or standard of care) will be analyzed as recorded on eCRF (also refer to Section 8 of the Study Protocol for definitions).

Clinically significant adverse drug reactions (ADRs) are treatment-emergent drug-related AEs and SAEs (as discussed above).

If a patient experiences more than one TEAE within a preferred term, the patient will be counted only once in the calculation of incidence of TEAE within that preferred term. Similarly, if a

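### The SAE analysis is said to cover all SAEs after first dose, but every by-arm SAE summary named in SAP 7.12.1 is limited to treatment-emergent SAEs

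*SAP*

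**What the plan says.** Two sections state the scope of the SAE analysis. SAP 7.1.3 gives the adverse event window and adds: "However, SAEs will include all the serious adverse events collected after the first dose". SAP 7.12 gives the window again and adds: "However, serious adverse events analysis will include all the serious adverse events collected after the first dose". Neither sets an end date for SAEs.

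Section 7.12.1 then defines categories and outputs. A treatment-emergent event is one that starts or worsens from first dose onward, within a window closed by whichever of three limits comes first: "the earliest of the following 1) the date for the Day 58; 2) date of early discontinuation from study, or 3) data cutoff date". There is no exception for serious events. The post-treatment category is defined by one limit only: "All adverse event started after study day 58 will be considered post-treatment".

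The SAE summaries named in 7.12.1 are:

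- "Treatment-related TEAE, serious TEAE and treatment-related serious TEAE will be summarized by MedDRA System Organ Class and PT, and the maximum severity"
- "The frequency of treatment-emergent serious adverse events (TESAEs) will be summarized by arm, SOC, and preferred term"
- for sites supplied with the device by the sponsor, "All device-related TE-SAEs will be summarized by treatment arm"

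SAEs and deaths without the treatment-emergent restriction are given as patient listings, and the SAE listing carries a treatment-emergent flag. Deaths are also analysed in 7.11.2.2, where "Survival status will be collected up to Day 90 +/- 30 days". That section plans a by-arm count, survival time, Kaplan-Meier estimates to Day 90 and a Cox hazard ratio.

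**The concern.** Two stated rules give different sets of SAEs. The scope statements include every collected SAE after first dose. The tables in 7.12.1 include only those in the treatment-emergent window. A programmer working from 7.12.1 leaves out of every named by-arm table some events that 7.12 says are analysed.

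A listing is a weak substitute. Allocation is 2:1, so counting listed events without denominators misleads, and the trial is open-label, so the choice of window is better fixed before database lock. The number of patients with treatment-emergent SAEs is also a secondary endpoint (SAP 5.2.2). The exemption in 7.1.3 comes directly after the treatment-emergent window, so it can be read as widening that window for SAEs. Two analysts could then report different counts for one endpoint.

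The categories have a related gap. Section 7.12.1 sorts adverse events into prior, treatment-emergent and post-treatment, but the last two do not meet when a patient leaves the study before Day 58.

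**Working it through.** The plan gives no figure to reproduce, so the check sets the sections side by side.

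**Step 1: scope.** 7.1.3 and 7.12 both start SAEs at first dose, with no end. For the control arm, 7.1.1 uses the randomization date as the first dose date.

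**Step 2: outputs.** 7.12.1 names four SAE summaries: serious TEAEs, treatment-related serious TEAEs, TESAEs by arm, system organ class and preferred term, and device-related TE-SAEs. All four are restricted to treatment-emergent events. None covers all SAEs after first dose.

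**Step 3: test cases.** These are illustrations and assume that the event is collected.

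| SAE | In the SAE analysis (7.1.3, 7.12)? | Category in 7.12.1 | In a named by-arm SAE table? |
|---|---|---|---|
| Starts by Day 58, patient still in study | Yes | Treatment-emergent | Yes |
| Starts by Day 58, patient still in study; fatal on Day 70 | Yes | Treatment-emergent, by start date | Yes |
| Starts on Day 70 | Yes | Post-treatment | No, listed only |
| Patient leaves on Day 10; SAE starts on Day 12 | Yes | None | No, listed only |

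The third and fourth rows show the mismatch, and the fourth also shows the category gap. The second row shows that a late death does not by itself take an SAE out of the tables, because classification is by start or worsening date and not by outcome date.

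**Step 4: which limits matter.** Day 58 and early discontinuation are the limits that separate the two counts in these cases. Data cutoff is the third limit. It would normally bind both counts alike if all tables are drawn from the same data cut.

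**Step 5: deaths.** 7.11.2.2 reports deaths by arm whatever the category of the underlying event. What the text does not name is a by-arm system organ class and preferred term table that would include a fatal SAE starting outside the window. Cause of death is listed only.

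**The case against.** The strongest reply is that the exemption can be read as extending the treatment-emergent window for serious events. On that reading the TESAE tables already hold all SAEs, and 7.12 also promises that safety variables will be tabulated. The mock tables are in a separate document that is not at hand and may include an all-SAE table. This stands in part: one can say only that the text of 7.12.1 names no such table. But 7.12.1 gives its own definition with explicit limits and no exception, so the reading needs a change to the text.

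A second reply is that the secondary endpoint is defined on treatment-emergent SAEs, is tabulated by arm, and is one of a set of analyses that are all descriptive. That is fair and lowers the importance. Day 58 is also 58 − 5 = 53 days after the last planned dosing day.

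Three stronger readings are tempting but not supported:

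- A reader might infer that fatal SAEs are only listed. They are not: 7.11.2.2 summarizes deaths by arm, and fatal SAEs with onset inside the window enter the TESAE tables.
- A reader might infer that deaths in the safety tables will disagree with the mortality analysis. Section 7.12.1 plans no death table, only a listing, and a TESAE table and a Day 90 survival analysis have different stated windows.
- A reader might take Days 59 to 90 (90 − 58 = 32 days; 32/90 = 36%), or Days 59 to 120 (62 days), as the size of the loss. That assumes SAEs are collected that long. Section 7.11.2.2 promises only survival status, and a share of days is not a share of events. The headings of 6.4.4 and 6.4.5 give a study period to Day 28 and follow-up of up to 30 days after the end-of-study visit. If that visit is Day 28, follow-up ends at 28 + 30 = Day 58, the same as the treatment-emergent limit.

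That withdrawal differs by arm, and so truncates SAEs unequally, is possible in an open-label trial, but nothing in the SAP shows it.

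**Conclusion.** The point holds in a limited form. The SAE scope in 7.1.3 and 7.12 and the SAE summaries named in 7.12.1 do not agree, and as written a collected SAE starting outside the treatment-emergent window reaches only a listing. The category gap between early discontinuation and Day 58 is also real.

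The number of SAEs affected cannot be stated. It depends on how long, and after what kind of discontinuation, SAEs are collected; the SAP leaves this to the protocol, which is not at hand. If nothing is collected after Day 58 or after study exit, the two counts coincide. The SAP does allow for such events, since it defines a category for onset after Day 58 and writes the SAE exemption twice.

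Severity is minor and confidence moderate, because the exemption can be read more than one way and the table shells were not available.

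**What to change.** Reconcile 7.1.3, 7.12 and 7.12.1 before database lock:

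1. Add to 7.12.1 a by-arm table, by system organ class and preferred term, of all SAEs with onset on or after first dose (randomization in the control arm). Treat worsening as the TEAE definition does, so that the TESAE table is a subset of the new one.
2. Keep the Day 58-limited TESAE table and label it as the count for the secondary endpoint in 5.2.2.
3. Define post-treatment AEs as those starting after the end of the treatment-emergent period, whichever of the three limits ended it, so that every AE falls in one category.

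The cost is a few lines of SAP text and one added table from data already collected. The downside is that the report will carry two SAE counts, so each title needs to state its window.

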7.12.1 Adverse Event

All adverse events will be coded using Medical Dictionary for Regulatory Activities (MedDRA) version 23.0 (or later). Adverse events will be categorized as prior events, treatment emergent adverse events, and post treatment adverse events:

- Prior Events includes all adverse events with a start date before the first dose of the study drug regardless of the end date.
- Treatment-emergent adverse events (TEAE) are defined as adverse events with a start date (or date of worsening) on or after the first dose of the study drug and no later than the earliest of the following 1) the date for the Day 58; 2) date of early discontinuation from study, or 3) data cutoff date.
- All adverse event started after study day 58 will be considered post-treatment.

All TEAE will be summarized by treatment arm and presented by:

- 1) system organ classification and preferred term (PT);
- 2) PT;
- 3) system organ classification, PT and the maximum severity.

Treatment-related TEAE, serious TEAE and treatment-related serious TEAE will be summarized by MedDRA System Organ Class and PT, and the maximum severity. SAEs and deaths will be listed by patient.

For patients at sites where Aerogen devices were supplied by PTX, the following analyses will be performed:

- All device-related TEAEs will be summarized by treatment arm;
- All device-related TE-SAEs will be summarized by treatment arm;
- All device-related AEs will be listed by patient.

The frequency of treatment-emergent serious adverse events (TESAEs) will be summarized by arm, SOC, and preferred term. Severity (using CTCAE) and relationship of TEAEs to treatment (sargramostim, sargramostim inhalation device or standard of care) will be analyzed as recorded on eCRF (also refer to Section 8 of the Study Protocol for definitions).

Clinically significant adverse drug reactions (ADRs) are treatment-emergent drug-related AEs and SAEs (as discussed above).

If a patient experiences more than one TEAE within a preferred term, the patient will be counted only once in the calculation of incidence of TEAE within that preferred term. Similarly, if a

patient experiences more than one TEAE within a system organ class, the patient will be counted only once in the calculation of incidence of TEAE within that system organ class. If a patient experiences more than one TEAE within a preferred term (or system organ class), the occurrence with the highest severity will be used in the calculation of the incidence of TEAE within that preferred term (or system organ class) with regards to severity. If a patient experiences more than one TEAE within a preferred term (or system organ class), the occurrence considered most closely related to study drug will be used in the calculation of the incidence of TEAE with that preferred term (or system organ class) with regards to relationship .

Data listings for all AEs, and for serious AEs, will be provided with flags for TEAE, relatedness and CTCAE severity.

7.12.2 Laboratory data

Laboratory data, as performed and collected as part of SOC in both arms (see_Section 10 in the Study Protocol), will be collected and include the following:

- Hematology laboratory parameters: complete blood count with differential, hemoglobin, hematocrit, and absolute counts for white blood cells, platelets, neutrophils, lymphocytes, eosinophils and monocytes.
- Chemistry laboratory parameters: albumin, amylase, lipase, BUN, creatinine, ALT, AST, LDH, serum alkaline phosphatase, direct and total bilirubin, glucose, total protein, sodium, potassium, chloride, bicarbonate, calcium and uric acid.
- Required laboratory measurements of ferritin, d-dimer and C-reactive protein should also be collected at screening, Days 1-6 and any other time it is performed as part of SOC.

• Immune profiling, if performed, including CD4+, CD8+, HLA-DR, IL-6, IL-1, GM-CSF Descriptive statistics for baseline value, actual value at a given visit, and change from baseline to each scheduled postbaseline visit will be provided by arm for the clinical hematology, chemistry laboratory, ferritin, d-dimer, CRP, and immune profiling (where available) tests described above. In addition, the neutrophil/lymphocyte ratio will also be summarized and listed. Baseline for these tests is defined as the last assessment prior to administration of study drug (see Section 7.1.2). Conventional Units will be used for reporting the laboratory test results.

Serum pregnancy test results will be listed. Values for any chemistry, hematology, ferritin, ddimer, CRP, and immune profiling values outside the clinical reference ranges (where available) will be flagged on the individual patient data listings.

7.12.3 Physical Examination

Physical examination findings will be listed by arm and patient.

7.12.4 Vital Signs

Vital signs (including temperature, respiratory rate, and blood pressure and pulse) will be measured during the Screening visit, Treatment period Days 1-5, Post-treatment period at Day 6 or day of discharge (whichever is earlier), Day 28, and Day 90.

Baseline for vital signs is defined as the last assessment prior to administration of study drug (see Section 7.1.2).

All vital sign data including unscheduled records will be listed. Unscheduled records will be excluded from the summary statistics. Vital sign data including baseline value, actual value at a given visit, and change from baseline to each post-baseline visit will be summarized by arm and timepoint.

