7.11.2.1 Change in Ordinal Scale

Ordinal scale will be assessed at the Screening/Baseline, during the 5 days of treatment administration, and at any days where the patients are hospitalized through Day 28 and at Day 90. Baseline for the following analyses is defined as the last ordinal scale prior to administration of study drug. The number of patients with an improvement in the ordinal scale, defined as a change from baseline of ≥ 2 points, will be tabulated.

A MMRM model will be used to evaluate the change in ordinal scale, in which the change of ordinal scale from baseline on each timepoint of interest will be included as dependent variable and treatment, timepoint (categorical), and treatment-by-timepoint as fixed effects, patient as random effect, and the baseline value as a continuous covariate. An unstructured covariance matrix will be used for the MMRM analysis, unless the model does not converge, in which case the compound symmetry will be used.

Descriptive statistics for the overall treatment effect based on the MMRM model will include the least-squares (LS) mean difference, LS mean change from baseline for each treatment arm, their corresponding 95% CIs, and the p-values associated with the treatment difference compared to SOC. In addition, LS Means for the treatment differences at each timepoint of interest between treatment arms may also be provided with the same set of statistics derived from the same MMRM model defined above based on the MMRM estimates.

Additionally, the non-model based descriptive statistics for the corresponding change from baseline (overall) in the ordinal scale at each visit or timepoint of interest, change from baseline and maximum change from baseline will be evaluated and summarized by treatment arm. Except as noted in Section 7.1.1, unscheduled records will be excluded from the summaries at specific timepoints but will be included in the maximum change from baseline.

All available values of the ordinal scale, including change from baseline and maximum change from baseline will be listed by arm and patient. Refer to Appendix C of the Study Protocol for the ordinal scale categories.

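### The by-arm vital-sign and laboratory tables work by visit, and no worst-value or abnormality summary is planned to capture off-schedule readings

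*SAP*

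**What the plan says.** **Vital signs (SAP 7.12.4).** After screening, the schedule is "Treatment period Days 1-5, Post-treatment period at Day 6 or day of discharge (whichever is earlier), Day 28, and Day 90". The by-arm output is the value at each visit and the change: "change from baseline to each post-baseline visit will be summarized by arm and timepoint". Off-schedule readings are kept out of these tables ("Unscheduled records will be excluded from the summary statistics") and appear elsewhere: "All vital sign data including unscheduled records will be listed". No minimum, maximum or threshold summary is named.

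**Laboratory data (SAP 7.12.2).** Laboratory data are collected as they arise under standard of care, with ferritin, d-dimer and CRP required at screening and on Days 1-6. For the by-arm tables, "change from baseline to each scheduled postbaseline visit will be provided by arm". Values outside the reference range "will be flagged on the individual patient data listings". No shift table, grade table, worst value or abnormality count by arm is named.

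**Analysis period (SAP 7.1.3).** "The analysis period used for abnormalities in laboratory evaluations is defined as the period from the date of the first dose", and it can run to Day 90. Section 7.12 repeats the Day 90 limit.

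**Efficacy, for contrast (SAP 7.11.1.1 and 7.11.2.1).** For the P(A-a)O₂ gradient and the ordinal scale, "unscheduled records will be excluded from the summaries at specific timepoints but will be included in the maximum change from baseline". In both places the sentence opens with an exception for the relabelling rule in 7.1.1.

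**The concern.** In hospitalized patients with acute hypoxemia, extra vital signs and blood tests are likely to be taken when a patient is getting worse. A table of values at fixed visits is not designed to show those readings. A short-lived excess in one arm, for example in blood pressure, pulse, respiratory rate, liver tests or platelets, could occur between visits and leave no trace in any by-arm vital-sign or laboratory table. If the arms differ in length of stay, the amount left out may differ by arm as well.

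The SAP describes all its analyses as descriptive (7.1, 7.2), so the tables are themselves the safety result. About 80 patients on sargramostim and 40 on standard of care alone are planned. Comparing the arms by hand from listings is slow and easily incomplete.

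**Working it through.** The SAP states no figure on this point to reproduce. The check is a day count and a comparison of sections.

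**1. Day count for vital signs (inputs from 7.12.4).**
- Scheduled days within Days 1-28: Days 1-5 (5) + Day 6 (1) + Day 28 (1) = 7.
- Days without a scheduled timepoint: 28 − 7 = 21. These are Days 7-27 (27 − 7 + 1 = 21).
- As calendar days, 21/28 = 75%.
- Day 14 is the only day in that window that 7.1.1 names as a visit. If relabelling applies to vital signs, 21 − 1 = 20 days remain without a named visit.

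**2. What the day count does not measure.** The SAP gives no length of stay and does not say how many vital signs are recorded on Days 7-27. As an illustration only, a patient in hospital through Day L (L from 6 to 27) has L − 6 inpatient days off the schedule:

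| L (assumed) | Off-schedule days | Share of inpatient days, (L − 6)/L |
|---|---|---|
| 6 | 0 | 0% |
| 8 | 2 | 25% |
| 10 | 4 | 40% |
| 12 | 6 | 50% |
| 20 | 14 | 70% |

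These are shares of days under assumed stays. They are not shares of readings and do not apply to laboratory data.

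**3. Routes by which an off-schedule value could reach a by-arm display.**
- *Relabelling (7.1.1).* An unscheduled assessment dated the same as another visit may take that visit's label, and other handling is allowed. The rule is permissive. The two efficacy sections refer to it as an exception; 7.12.4 does not, so it is unclear whether it overrides the exclusion of unscheduled vital signs. A relabelled value would enter a by-visit summary, not a worst-value one.
- *WBC and lymphocytes (7.11.2.6).* These are taken on any hospital day through Day 28 and at Day 90, and a table of normal, low and high results at available visits is planned. It covers two parameters, and its layout by arm is not stated.
- *NEWS-2 and SOFA (7.11.3.1, 7.11.3.2).* These are exploratory. Under 7.11 they are summarized only if the primary and secondary endpoints show meaningful results.
- *Patient profiles (7.12.6).* These show key laboratory parameters for patients with SAEs, discontinuation due to an AE, or death. They are per patient, and vital signs are not named.
- *AE tables (7.12.1).* These are by arm, but show only what was reported as an adverse event, in an open-label study.

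**4. Side by side.** Section 7.1.3 sets a period for laboratory abnormalities, but 7.12.2 names no by-arm analysis of abnormalities that uses it. Sections 7.11.1.1 and 7.11.2.1 pair the exclusion of unscheduled records with a maximum that includes them. Section 7.12.4 has the exclusion without the maximum, and 7.12.2 has no maximum either.

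**The case against.** **The exclusion itself is sound practice.** Keeping event-driven readings out of by-visit summaries avoids mixing them with readings taken at planned times. This stands, and the by-visit tables need no change. The gap is the missing companion summary.

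**A reader might infer that no off-schedule reading can reach any by-arm table.** The SAP does not support that. Section 7.1.1 may admit readings dated on a visit day, and 7.11.2.6 may admit WBC and lymphocyte values from any hospital day.

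**A reader might infer that unscheduled laboratory records are expressly excluded.** They are not. Section 7.12.2 limits change from baseline to scheduled visits; exclusion follows by inference. The section refers to the protocol for collection, and 7.11.2.6 suggests that hospital days after Day 6 may be scheduled laboratory days for some tests.

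**A reader might infer that 75% of vital-sign readings are lost.** The figure counts calendar days. Discharged patients have no inpatient readings, and the SAP does not show how many readings exist on Days 7-27.

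**The dosing window is covered.** Sargramostim is planned for 5 days, and vital signs are tabulated on Days 1-5 and at Day 6 or discharge. This stands for planned readings. It does not help with an extra reading taken on those days during a deterioration, unless relabelling applies.

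**Table shells are in a separate document.** They might contain worst-value or shift displays, which cannot be checked here. The SAP text does not commit to any.

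**Conclusion.** The point holds as a modest, inexpensive improvement. Vital signs and laboratory values are compared between arms only by visit or timepoint. The SAP commits to no by-arm worst-value or abnormality summary for either, under any reading of its text. Apart from the two possible routes in 7.1.1 and 7.11.2.6, off-schedule values reach only listings or patient profiles. The AE tables and the conditional NEWS-2 and SOFA summaries do not replace the missing display.

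The one firm number is that 21 of the first 28 calendar days have no scheduled vital-sign timepoint. The share of readings affected, and whether it differs by arm, cannot be derived from the SAP. The practical importance rests on the assumption that off-schedule readings are taken more often when patients are unwell.

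**What to change.** 1. Keep the by-visit tables in 7.12.2 and 7.12.4 as they are.
2. Add, by arm, each patient's lowest and highest post-baseline value for every vital sign and laboratory parameter, from scheduled and unscheduled records together, over Days 1-6 and over Days 1-28.
3. Add, by arm, the number of patients with any laboratory value outside the reference range (or of CTCAE grade 3-4) over the same two windows. This gives 7.12.2 an abnormality analysis to go with the period defined in 7.1.3.
4. Show the number of readings per patient by arm beside these tables.
5. State in 7.12.4 whether the 7.1.1 relabelling rule applies to vital signs.

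The cost is some SAP wording and a few tables from data already collected and listed. The downside is that extremes depend on how often a patient is monitored: more readings give a higher maximum and a lower minimum. The reading counts in item 4 make unequal monitoring visible, but do not correct for it.
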